5.6 Duration of Follow Up

Participants will be followed for **3 years** after removal from protocol therapy or until progression to active symptomatic MM or need for new therapy, whichever occurs first. Participants removed from protocol therapy for unacceptable adverse event(s) will be followed until resolution or stabilization of the adverse event.

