5.7 Criteria for Taking a Participant Off Study

Participants will be removed from study when any of the following criteria apply:

- Lost to follow-up
- Withdrawal of consent for data submission
- Death
- Progression to active myeloma and subsequent treatment

The reason for taking a participant off study, and the date the participant was removed, must be documented in the case report form (CRF).

CONFIDENTIAL

This document is confidential. Do not disclose or use except as authorized.

A Treatment Ended/Off Study Form will be filled out when a participant is removed from protocol therapy. This form will be provided by the lead site. External sites should submit the form to the Research Project Manager.

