6. DOSING DELAYS/DOSE MODIFICATIONS

6.1 Recommended Criteria for Beginning or Delaying a Subsequent Treatment Cycle

Patients must meet eligibility criteria on Cycle 1 Day 1 to begin treatment. There are no pre-treatment criteria to begin a new cycle of nivolumab.

For a new cycle of treatment with lenalidomide to begin, the patient must meet the following criteria:

- ANC must be $\geq 1,000/\mu\text{L}$.
- Platelet count must be $\geq 50,000/\mu\text{L}$.
- All other clinically significant, study drug related non hematologic toxicity must have resolved to \leq Grade 1 or to baseline condition

If the participant fails to meet the above-cited criteria for initiation of a new cycle of treatment on day 1 of the cycle, dosing of all medications should be delayed for 1 week. At the end of that time, the participant should be re-evaluated to determine whether the above criteria have been met. If the participant continues to fail to meet the above-cited criteria, delay therapy and continue to re-evaluate. The maximum delay for toxicity related to study treatment before treatment is permanently discontinued will be 3 weeks. If a delay of > 3 weeks is clinically necessary, and the patient is showing benefit from treatment, the patient may continue on study after discussion and approval by the Principal Investigator.

If any one of the study medications is permanently discontinued for any reason including toxicity, or FDA mandate, the patient may remain on the study at the discretion of the principal investigator.

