6.3 Lenalidomide

Hematologic Toxicities: For adverse hematologic events that are considered possibly, probably or definitely related to Lenalidomide, the following criteria for retreatment and dose modification should be followed unless discussed and approved first by the overall principal

CONFIDENTIAL

This document is confidential. Do not disclose or use except as authorized.

investigator. The treating investigator should determine the clinical significance of laboratory values and attribution to study medications before a treatment decision is made. All instances where lenalidomide is held, the dose will be considered missed, and will not be made up.

Non Hematologic Toxicity: For adverse non hematologic events that are considered to be possibly, probably or definitely related to Lenalidomide, the following criteria for retreatment and dose modification should be followed unless discussed and approved first by the overall principal investigator. The treating investigator should determine the clinical significance of laboratory values or radiographic findings and attribution to study medications before a treatment decision is made. All instances where lenalidomide is held, the dose will be considered missed, and will not be made up.

Dose delays and modifications should be made as indicated in the following table(s) unless first discussed with the Overall PI. The descriptions and grading scales found in the revised NCI Common Terminology Criteria for Adverse Events (CTCAE) version 4.0 will be utilized for dose delays and dose modifications. A copy of the CTCAE version 4.0 can be downloaded from the CTEP website

http://ctep.cancer.gov/protocolDevelopment/electronic_applications/ctc.htm.

Table 12 Lenalidomide Hematologic Toxicities

CTCAE 4.0 Category	CTCAE Grade	Lenalidomide Dose Modification
Absolute Neutrophil Count (ANC)¹	Grade 1 or Grade 2	Continue to treat- Do NOT OMIT and DO NOT REDUCE therapy
	Grade 3	Hold dose Administer Filgrastim Resume at same dose when ANC is \geq 1000 if neutropenia is the only hematologic toxicity If other hematologic toxicity \geq Grade 2 is present, reduce dose one level when ANC \geq 1000
	Grade 4	Hold dose Administer Filgrastim Resume therapy at one dose level lower when ANC is \geq 1000
Neutropenia with Fever ANC <1000 and temperature \geq 38.5° C or 101°F	Grade 3 or Grade 4	Hold dose Administer Filgrastim Reduce dose one level when ANC \geq 1000

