Thrombocytopenia	Grade 1 or Grade 2	Continue to treat- Do NOT OMIT and DO NOT REDUCE therapy

CONFIDENTIAL

This document is confidential. Do not disclose or use except as authorized.

Aspirin prophylaxis should be held if platelets are $\leq 50,000$	Grade 3 or Grade 4	
Provide platelet transfusion support Redraw platelets
 
If redrawn platelet value $\geq 50,000$ -> Do NOT OMIT and DO NOT REDUCE therapy
 
If redrawn platelet value $< 50,000$ continue to transfuse at the discretion of the investigator and hold therapy until platelets are $\geq 50,000$ on Day 1 or $\geq 30,000$ intracycle
 
Resume therapy at one dose level lower when the patient's platelets are $\geq 50,000$ on Day 1 or $\geq 30,000$ intracycle

	Grade 1 Grade 2 Grade 3	
Continue to treat- Do NOT OMIT and DO NOT REDUCE therapy Transfuse at the discretion of treating investigator

Anemia	Grade 4	
Hold treatment Transfuse Resume treatment when hemoglobin ≥ 8.0 g/dL DO NOT REDUCE therapy

¹ ANC can be calculated two ways: From the percentage of neutrophils: White Blood Count (WBC) x total neutrophils (polys% + bands%) x 10. From the absolute number of cells: (Absolute polys + Absolute bands) x 10.

Table 13 Lenalidomide Non Hematologic Toxicities

CTCAE 4.0 Category	CTCAE Grade	Lenalidomide Dose Modification
Infection or Viral Illness with ANC¹ ≥ 1000 Including herpes zoster reactivation	N/A	
Day 1 of Cycle: Delay cycle until infection/viral illness has resolved. Resume treatment at the same dose level. Do not dose reduce.
 
Intracycle: Hold lenalidomide for a maximum of 21 days to allow for recovery. Resume treatment at same dose level.
 
If patient has delay of greater than 21 days, the patient must come off-study

CONFIDENTIAL

This document is confidential. Do not disclose or use except as authorized.

Infection or Viral Illness with ANC¹ < 1000	N/A	
Day 1 of Cycle: Delay cycle until infection/viral illness has resolved. Administer filgrastim or equivalent as indicated.
 
Reduce one dose level when infection/virus has resolved, and ANC \geq1000
 
Intracycle: Hold lenalidomide for a maximum of 21 days. Reduce one dose level when infection/virus has resolved and ANC \geq 500
 
If patient has a delay of less than or equal to 21 days, dose reduce to next dose level. If patient has delay of greater than 21 days, the patient must come off-study

--	------------	---

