	Grade 4	Hold Lenalidomide until toxicity resolves to < grade 2 Resume therapy with one dose level reduction If treatment-related toxicity occurs on day one of the cycle, the cycle will be delayed. If patient has a delay of less than or equal to 21 days, dose reduce to next dose level. If patient has delay of greater than 21 days, the patient must come off-study

If the patient discontinues lenalidomide, he or she does is not required to come off protocol therapy.

Table 14 Lenalidomide Dose Reduction

Dose Level	Lenalidomide Dose
0	25 mg
-1	20 mg
-2	15 mg
-3	10 mg
-4	5 mg

If lenalidomide is reduced for any toxicity, the dose may not be re-escalated.

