5- A bone marrow biopsy is required within 6 weeks of registration. A bone marrow aspirate for clinical and research purposes is required pre-treatment and may be performed up to 28 days prior to registration. Both core and aspirate are required any time during the course of the study to confirm CR, and is also required at C7D1

6- Research bone marrow aspirate and biopsy at the same time as clinically indicated bone marrow biopsy and to confirm response.

CONFIDENTIAL

This document is confidential. Do not disclose or use except as authorized.

Local Protocol #: 16-242

Version Date: 23 January 2018

7- Peripheral blood samples for correlative studies may be done at any time pre-treatment, though baseline and C1D1 samples should be considered separate time points.

8-If C7D1 or confirmation of response BM aspirate and core biopsy was performed within 3 weeks of either timepoint, the procedure need not be repeated. At minimum, an aspirate sample is required

9- Disease assessment/response assessment is required each Day 1 starting with C2-If the participant's disease response is not followed primarily via a UPEP (24 hour urine collection) and Urine immunofixation, these tests may be done only at screening, end of treatment, and every 3 months during treatment.

10-A CD of scans at screening and end of treatment is required to be sent to the lead site for central review. Screening scans should be sent with the eligibility packet to the lead site- This requirement includes a full body skeletal survey in addition to spinal MRI OR the patient may have only a low dose PET CT

11- Follow-up should occur every 3 months (+/- 14 days) for up to 3 years after end of treatment.

12- Women of child-bearing potential must abide by revlimid REMS procedures and may require additional pregnancy testing as described in section 3.1.7.

13- Buccal swab may be collected at any time throughout the study but should be collected pre treatment on C1D1

14- Thyroid labs are required at screening, C3D1, C6D1 and every 3 cycles thereafter, at end of treatment, and at any time that it is clinically indicated

15- Alert Overall PI immediately if there is concern for cardiac toxicity (At minimum, the following should be performed: cardiology consult, EKG, echocardiogram, and labs CPK and troponin; refer to section 6.2.7 for more details)

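### Three Table 13 cells take a patient delayed over 21 days off study by default, against 6.1, 5.6 and 5.7; Tables 12 and 13 also differ on the mid-cycle ANC for restarting lenalidomide

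*Combined protocol and SAP*

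**What the plan says.** **Delay over 21 days.** In Section 6.3, Table 13, the cells for infection with ANC of 1,000 or more, infection with ANC below 1,000, and Grade 4 events under all other related toxicities each say: "If patient has delay of greater than 21 days, the patient must come off-study". The text before the tables qualifies them: "the following criteria for retreatment and dose modification should be followed unless discussed and approved first by the overall principal investigator". The note directly under Table 13 reads: "If the patient discontinues lenalidomide, he or she does is not required to come off protocol therapy".

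Elsewhere the protocol treats a long delay differently:

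- Section 6.1: "The maximum delay for toxicity related to study treatment before treatment is permanently discontinued will be 3 weeks". If a longer delay is clinically necessary and "the patient is showing benefit from treatment, the patient may continue on study after discussion and approval by the Principal Investigator".
- Section 5.6: participants are followed for 3 years "after removal from protocol therapy or until progression to active symptomatic MM or need for new therapy, whichever occurs first".
- Section 5.7: "Participants will be removed from study when any of the following criteria apply". Four reasons are listed: loss to follow-up, withdrawal of consent for data submission, death, and progression with subsequent treatment.
- Section 10, footnote 11: "Follow-up should occur every 3 months (+/- 14 days) for up to 3 years after end of treatment". Footnote 17 requires a response assessment at each of those visits.

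**ANC for restarting lenalidomide.** For infection with ANC below 1,000, Table 13 sets 1,000 on Day 1 of a cycle. Mid-cycle it sets 500, once the infection has resolved and with a reduction of one dose level. Table 12 sets 1,000 for Grade 3 ANC, Grade 4 ANC and neutropenia with fever, with no separate mid-cycle value. The nursing page asks for 1,000 on Day 15.

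**The concern.** The primary endpoint is progression-free status at 2 years, but protocol therapy lasts only 12 cycles. Most of the second year is therefore observed after treatment, and the endpoint depends on keeping patients under follow-up once therapy stops. A dosing table that takes a patient off study, when the governing sections would only take the patient off treatment, puts that observation at risk for a reason unrelated to consent or progression. Section 13.1.1 keeps every dosed patient in the analysis, including those lost within 2 years, so such a patient would stay in the analysis without an observed outcome.

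The ANC point is about dosing safety and consistency between sites. Two tables in one section can both apply to a neutropenic patient who has just had an infection, and they set different levels for resuming a drug whose hematologic toxicity the protocol manages by holds and dose reductions.

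**Working it through.** No figure in the plan is at issue, so the check compares provisions and adds one timing calculation.

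**Step 1. What happens after a delay of more than 21 days (3 weeks)?**

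| Source | Consequence |
|---|---|
| Table 13, three cells | Off study, unless the overall PI approves otherwise first |
| Section 6.1, default | Treatment permanently discontinued |
| Section 6.1, exception | Benefiting patient continues with PI approval |
| Note under Table 13 | Stopping lenalidomide need not end protocol therapy |
| Section 5.6 | Follow-up for 3 years after therapy ends, or until progression or new therapy |
| Section 5.7 | Dose delay is not among the four off-study reasons |
| Section 10, footnotes 11 and 17 | 3-monthly visits with response assessment after treatment |

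Only the Table 13 cells end participation because of a delay.

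**Step 2. Does the protocol distinguish the two terms?** Yes. Section 5.5 governs leaving protocol therapy and Section 5.7 governs leaving the study. The cardiac table in 6.2.7 refers to leaving protocol therapy when that is what it means.

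**Step 3. How much follow-up is at stake for one patient?** Inputs: 12 cycles of 28 days (Sections 1.3 and 5.1), a 21-day delay, and 2 years taken as 730 days. Assumption: no other delays.

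- Planned therapy: 12 × 28 = 336 days.
- Latest removal under the rule: 336 + 21 = 357 days.
- Shortfall to the endpoint: 730 − 357 = 373 days, or about four 3-monthly assessments.

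Removal in an earlier cycle leaves a larger gap. An earlier approved delay would push removal later and narrow it.

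**Step 4. ANC at which lenalidomide may restart.**

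| Situation | Day 1 | Mid-cycle |
|---|---|---|
| Table 13, infection with ANC below 1,000 | 1,000 | 500 |
| Table 12, Grade 3 ANC | 1,000 | 1,000 (no split) |
| Table 12, Grade 4 ANC | 1,000 | 1,000 (no split) |
| Table 12, neutropenia with fever | 1,000 | 1,000 (no split) |
| Nursing page | 1,000 | 1,000 (Day 15) |

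Table 12 does split the platelet level, at 50,000 on Day 1 and 30,000 mid-cycle. Its author therefore used a split where one was wanted, and did not use one for ANC.

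**Step 5. Can one patient meet both tables?** Yes. A patient with an infection, a temperature of at least 38.5 °C and an ANC below 1,000 meets the Table 12 fever row and the Table 13 infection row. If the infection resolves mid-cycle and the ANC recovers only to 500 to 999, the Table 13 criterion for restarting one level lower is met and the Table 12 criterion is not.

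**The case against.** The best reply on the first part is that off-study here loosely means off treatment. The 21 days match the 3 weeks in 6.1, which itself speaks of continuing on study when it means continuing treatment. Section 6.4 does the same for dexamethasone, and one form serves both for ending treatment and for leaving the study. Sections 5.6 and 5.7 and the calendar would then govern follow-up, with the PI override as a further safeguard. This reading is plausible, and it means loss of follow-up is possible rather than certain. It does not remove the conflict: 5.5 and 5.7 keep the terms apart, the override works case by case without correcting the default that a site reads, and even on this reading it is unclear whether all treatment stops or only lenalidomide.

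It is also fair to say that the three Table 13 categories without the off-study wording (allergic, renal/metabolic, gastrointestinal) are not free of a time limit, since 6.1 covers any treatment-related toxicity. They differ in the stated consequence, not in the limit.

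A reader might infer a measurable loss of power. The documents do not support one. They give no rate of delays over 21 days, and 13.1.1 does not say how patients without a 2-year outcome are counted. Accrual stopped in September 2017, so 39 or 41 patients may not have been reached. Keeping the cutoff of 24 successes with 41 patients would itself change the test, since P(X ≥ 24 | 41, 0.5) = 0.174. Nor can one say how many patients were still on therapy under this version, because no last-enrolment date is given, and no removal for delay is documented.

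On ANC, the 500 may be deliberate. It applies only after the infection resolves and at a lower dose, and the platelet row shows that a two-level rule is acceptable in this protocol. A cautious site would wait until both tables were satisfied, and the nursing page gives a Day 15 check rather than a restart rule after infection. All of this stands as a reason not to call 500 an error. The two tables still need to agree.

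**Conclusion.** Both inconsistencies are in the current text and should be corrected.

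The off-study default appears in three Table 13 cells and conflicts with 6.1, the note under the table, 5.6, 5.7 and calendar footnotes 11 and 17. Followed literally during therapy, it could leave at least 373 days before the 2-year endpoint unobserved for that patient, assuming no other delays. The number of patients affected and any effect on the trial's operating characteristics cannot be determined from the documents.

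The ANC restart level mid-cycle is 500 in one cell, against 1,000 in three Table 12 rows and on the nursing page. The conflict applies to patients who meet both tables with an ANC of 500 to 999. Which level is right is a clinical question that the documents do not settle.

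**What to change.** 1. In the three Table 13 cells, replace the off-study instruction with: discontinue lenalidomide unless the overall PI approves continuation under 6.1; continue on-study follow-up every 3 months per 5.6. For anyone already removed because of a delay, obtain 2-year progression status where consent allows. Cost: wording in three cells. The 3-monthly visits are already in the study calendar.
2. In Table 13, for infection with ANC below 1,000, set the mid-cycle restart level to 1,000 as the safer default. If the sponsor confirms that 500 is intended, keep it and align Table 12 and the nursing page with it. Cost: one threshold, and somewhat longer lenalidomide holds after infection if 1,000 is used.

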5.4.3 Neutropenia

- Blood counts will be monitored regularly as outlined in the protocol with additional testing obtained according to standard clinical practice. Neutropenia may be severe but has been manageable. Growth factor support is not required but may be considered according to standard clinical practice. Lenalidomide administration should be modified as per dose modification recommendations in the protocol when neutropenia occurs (see Section 6.3).

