Study Drug Administration	
Agent Administration Guidelines are found in Section 5.2
 
 • Nivolumab is given IV every other week on Days 1&15; Lenalidomide is PO Days 1-21; Dexamethasone is PO Days 1, 8, 15 for Cycles 1-6 ONLY • Nivolumab is given IV over 60 minutes (+/- 10 minutes); No standard premeds required, unless history of infusion reaction. A 60 min post-infusion observation period is suggested, especially during first 2 cycles, but not mandatory per protocol. • The drugs may be administered in any order. • Criteria to treat DAY 1: ANC\geq1,000; PLT\geq50; Other drug related, non-heme tox \leqGrade 1 or baseline. • Criteria to treat DAY 15: For Lenalidomide: ANC\geq1,000; PLT\geq30; Hgb\geq8 Other drug related less than Grade 3 or baseline. For Nivolumab: AST\leq90; ALT\leq156; Bilirubin\leq1.8; Creatinine\leq1.95 or \leq1.5 x baseline • Fasting is not required. • Lenalidomide capsules and Dexamethasone tablets should be swallowed whole, and should not be broken, chewed or opened. Administration should be at approximately the same time each day. If a dose is missed and less than 12 hours has elapsed since the missed dose, the patient may take the dose for that day. If more than 12 hours has elapsed since missing a dose at the normal time, the patient should not take the dose, but take the next dose at the normal time on the following day. If a dose is missed, it should be taken as soon as possible on the same day. If a dose is vomited, the dose should not be made up and the participant should continue with the regular schedule of the drug at the next dose.
Dose Mods & Toxicity	
Dose Modifications/Dosing Delay for Toxicity are outlined in Section
 
 • This protocol uses NCI CTCAE criteria, version 4.03 • There are no dose modifications for Nivolumab, there are dose reductions per protocol for Lenalidomide and Dexamethasone.
Con Meds	
Concomitant Therapy Guidelines are in Section 5.3.1
 
 • Stem cell mobilization and collection may be performed at time of best response or after 6 cycles of therapy. • Filgrastim is allowed, pegfilgrastim is NOT. • Transfusions and supportive care are allowed; bisphosphonate therapy included.

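### After a resolved neutropenic infection within a cycle, Table 13 lets lenalidomide restart at ANC 500 while Table 12 holds it until 1,000, the two can also differ on dose, and no text says which prevails

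*Combined protocol and SAP*

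**What the plan says.** Section 6.3 governs lenalidomide holds through two tables. Table 12 covers hematologic events, and Table 13 non-hematologic events, each when judged possibly, probably or definitely related to the drug.

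- **Table 13, infection or viral illness with ANC below 1,000, intracycle:** "Hold lenalidomide for a maximum of 21 days. Reduce one dose level when infection/virus has resolved and ANC" is at least 500. The Day 1 rule in the same row requires 1,000. A delay beyond 21 days takes the patient off study.
- **Table 12, ANC grade 4:** "Resume therapy at one dose level lower when ANC is" at least 1,000. Grade 3 also releases at 1,000: at the same dose if neutropenia is the only hematologic toxicity, and one level lower if another of at least grade 2 is present.
- **Table 12, fever row:** "Neutropenia with Fever ANC <1000 and temperature" of at least 38.5 °C. Release is at 1,000, one level lower.
- **Table 12, platelets:** "continue to transfuse at the discretion of the investigator and hold therapy until platelets are" at least 50,000 on Day 1 or 30,000 intracycle. The ANC rows contain no such split.
- **Special nursing considerations page:** the line headed "Criteria to treat DAY 15: For Lenalidomide" asks for ANC of at least 1,000 and platelets of at least 30.

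On departures, Section 6.3 says "the following criteria for retreatment and dose modification should be followed unless discussed and approved first by the overall principal investigator". It does not rank the tables. Section 5.4.3 sends neutropenia to Section 6.3 as a whole and names no table.

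**The concern.** The Table 13 row is itself defined by a low ANC, so one patient can fall under both tables. For ANC 500-999 after the infection has cleared, one table permits dosing and the other continues the hold. Two sites, each following Section 6.3 as printed, could treat the same patient differently. The looser instruction applies just after a neutropenic infection, to a drug whose neutropenia Section 5.4.3 describes as possibly severe, although manageable so far. What is at stake is dosing safety and consistency between sites.

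**Working it through.** The conflict itself is a matter of text. Arithmetic is needed only for the cost of the fix and the remaining exposure.

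**Step 1: when both tables apply.** Table 13 needs the infection to be at least possibly related to lenalidomide. Table 12 needs the low ANC to be at least possibly related. The treating investigator decides attribution. If the low ANC is put down to the infection alone, only Table 13 applies and there is no conflict between the tables.

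**Step 2: restart level, both events attributed, infection resolved, mid-cycle.**

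| ANC at reassessment | Table 12 | Table 13 | Nursing Day 15 line |
|---|---|---|---|
| below 500 | hold | hold | do not treat |
| 500-999 | hold | restart one level lower | do not treat |
| 1,000 or more | restart | restart one level lower | ANC criterion met |

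Only the middle row conflicts. Cycle-start rules (Section 6.1 and the Day 1 part of the Table 13 row) all use 1,000 and agree.

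**Step 3: restart dose once ANC reaches 1,000.**

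| Table 12 situation | Table 12 dose | Table 13 dose | Agree? |
|---|---|---|---|
| Grade 4 | one level lower | one level lower | yes |
| Neutropenia with fever | one level lower | one level lower | yes |
| Grade 3 plus another hematologic toxicity of at least grade 2 | one level lower | one level lower | yes |
| Grade 3 alone, no fever at the Table 12 cut-off | same dose | one level lower | no |

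Waiting for 1,000 and then reducing one level therefore satisfies both tables in the first three situations but not the fourth. Reductions cannot be reversed (note to Table 14).

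**Step 4: cost of waiting for 1,000.** Lenalidomide is dosed on Days 1-21 (Section 8.2.7). Let the first missed dose be on Day d, from 2 to 21. Suppose the Table 13 restart condition is met on Day d + 1 and ANC then stays at 500-999 through Day 21. Extra missed doses = 21 − d:

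- d = 2: 21 − 2 = 19
- d = 8: 21 − 8 = 13
- d = 15: 21 − 15 = 6
- d = 21: 0

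The first figure is an extreme. It needs an infection that clears in one day and an ANC that then stalls for the rest of the dosing period, although Table 12 directs filgrastim.

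**Step 5: the 21-day limit.** If rest days count and the next cycle starts on Day 29, the time from Day d to the next Day 1 is 29 − d: 27 days at d = 2, 22 at d = 7, 21 at d = 8. Within the cycle, a hold can pass 21 days only if it began on Days 2-7.

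**Step 6: remaining exposure after this version (23 January 2018).** Accrual stopped in September 2017, so take 30 September 2017 as the latest possible start. Cycle 12 Day 21 is treatment day 11 × 28 + 21 = 329, which is 328 days after the first dose: 24 August 2018, or 213 days after the version date. For a last start 328 or more days before the version date, nothing remains. The documents do not give the last start date, so the range is 0 to 213 days, assuming no delays.

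**The case against.** The strongest reply is that the Table 13 row is the only one written for infection and ANC below 1,000 together, with its own hold, ANC level, dose and time limit, so it should govern as the more specific rule. Its 1,000 on Day 1 and 500 intracycle also parallel the platelet split in Table 12, which suggests that 500 was deliberate. Part of this stands: 500 may well be intended, and a reader who infers a misprint goes further than the documents allow. But no text gives the row priority. Table 12's neutropenia-with-fever row can describe the same patient just as specifically and requires 1,000.

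A second reply is that doubtful cases can go to the overall principal investigator. That approval is for departures from the criteria, and a site applying Table 13 as printed has no reason to think that it is departing from anything.

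A third reply is that the nursing line is a Day 15 check, not a rule for restarting after infection. That is fair. It shows that a mid-cycle staff instruction relaxes platelets but not ANC; it does not settle precedence.

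Two stronger readings are tempting. A reader might infer that every lenalidomide-related infection with ANC below 1,000 meets contradictory tables. It does not, because Table 12 applies only when the low ANC is also attributed to the drug. A reader might also infer that the cautious course, waiting for 1,000 and reducing, always complies with both tables. Step 3 shows that it does not.

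**Conclusion.** The contradiction is real but narrow. It needs both the infection and the low ANC to be judged at least possibly related to lenalidomide, resolution of the infection within the cycle, and ANC of 500-999. A separate disagreement on dose exists for isolated grade 3 neutropenia without fever. The documents give no count of patients in either group; few are likely. Remaining planned lenalidomide dosing after this version may be nil and is at most about 213 days under the assumptions shown. It need not be nil, because Section 5.1 lets patients stay on lenalidomide after nivolumab is stopped.

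The point bears on dosing safety and uniformity. Sample size, endpoint and primary analysis are not affected. It should be corrected because the remedy is small and the patient concerned has just recovered from a neutropenic infection.

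**What to change.** Change the intracycle restart level in the Table 13 row for infection with ANC below 1,000 from 500 to 1,000. Add one sentence: for such an infection, this row governs the restart dose, one level lower. The number alone is not enough, because it leaves the dose disagreement in place. The nursing page then needs no change.

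If 500 is intended, state instead that Table 13 overrides Table 12 on both ANC level and dose after a resolved infection, and carry the exception to the nursing Day 15 line.

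The cost of the higher level is a longer hold, and Section 6.3 is explicit about lost doses: "All instances where lenalidomide is held, the dose will be considered missed, and will not be made up". Nineteen in one cycle is the upper bound from Step 4. Slow recovery from a hold begun on Days 2-7 could reach the row's 21-day limit. Section 6.1 softens this by allowing longer delays with the principal investigator's approval when the patient is benefiting, and Section 6.3 says that stopping lenalidomide does not by itself end protocol therapy. Under either version, patients with isolated grade 3 neutropenia without fever take a permanent one-level reduction that Table 12 alone would not impose.
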